### 6.3 Withdrawal criteria

Subjects are free to withdraw from the study at any time, without prejudice to their continued care.

Subjects should be withdrawn from the study if any of the following events occur:

1. Subject withdraws his/her consent.
2. There is confirmation of a pregnancy during the study, as evidenced by a positive pregnancy test.
3. The Sponsor or a regulatory agency requests withdrawal of the subject.

#### Subjects withdrawn from study treatment:

Subjects should be withdrawn from all study treatment if any of the following events occur:

4. Subject develops an illness that in the opinion of the Investigator would interfere with his/her continued participation, if the risk of continuing participation outweighs the potential benefit.
5. Subject considered as having either a suspected new LTBI or who develop active TB or NTMB infection during the study (including but not limited to, conversion demonstrated by interferon-gamma release assay [IGRA] or other diagnostic means) must be immediately discontinued from study medication, and an unscheduled visit must be conducted as soon as possible, but not later than the next regular visit.

The subject must be permanently withdrawn if further examinations result in a diagnosis of active TB, or if the subject is diagnosed with LTBI with no initiation of prophylactic treatment, prematurely discontinues prophylactic treatment, or, in the opinion of the Investigator or Sponsor, is noncompliant with prophylactic TB therapy.

Confirmed active TB is a SAE and must be captured on an SAE Report Form and provided to the Sponsor in accordance with SAE reporting requirements. As with all SAEs, periodic follow-up reports should be completed as per protocol requirements until such time as the TB infection resolves. Additional information on TB policies is provided in Section 12.6.5.

6. Subject is noncompliant with the study procedures or medications, which may present a risk to the safety of the subject, in the opinion of the Investigator.
7. Subject uses prohibited concomitant medications, as defined in this protocol (Section 7.8.2), that may present a risk to the safety of the subject in the opinion of the Investigator and the Medical Monitor. This includes subjects who start a biologic other than bimekizumab as described in Section 5.1.4.
8. Subject develops laboratory abnormalities (with or without clinical symptoms) of ALT or AST as defined in Section 6.3.1; neutropenia  $<0.5 \times 10^9/L$ ; or lymphopenia  $<0.5 \times 10^9/L$ . Any laboratory value or change judged to be clinically significant by the Investigator should prompt consideration of whether the subject should continue on IMP. For clarification, laboratory values that are markedly abnormal as per Table 19-2 and Table 19-3 will be flagged to the Investigator and to the medical monitor but do not trigger mandatory withdrawal unless listed above. (Refer to Section 6.3.1 for withdrawal criteria in relation to potential drug-induced liver injury [PDILI].)
9. Subject has active suicidal ideation as indicated by a positive response (“Yes”) to Questions 4 or 5 or to the suicidal behavior questions of the “Since Last Visit” version of the self-rated eC-SSRS. The subject should be referred immediately to a Mental Healthcare Professional and must be withdrawn from the study.
10. Subjects with a HADS-D score  $\geq 15$  must be withdrawn. Any subject who develops a HADS-D score of  $>10$  during the study should be referred immediately to a Mental Healthcare Professional for further evaluation and potential withdrawal by the Investigator.
11. Subjects with newly diagnosed inflammatory bowel disease (IBD) or with IBD flares during the study must:
  - Be referred, as appropriate, to a health care professional treating IBD, such as a gastroenterologist
  - Discontinue IMP and be followed-up until resolution of active IBD symptoms

If IBD flares increase in severity or frequency during the study, the Investigator should use clinical judgment in deciding whether the subject should continue in the study and contact the Medical Monitor and UCB study physician to confirm the subject's suitability for continued participation in the study.

In an attempt to prevent missing data during the study, efforts will be made to collect data from subjects that withdraw early from the study (NRC, 2010). If a subject withdraws from study treatment for any of the above criteria (#4 through #10) prior to Week 12, they will be asked to return for the study assessments 12 weeks after the first dose (ie, Week 12 Visit) and for the SFU Visit (20 weeks after last dose administration). These data will be used in a sensitivity analysis which is described in Section 15.7. If any of these criteria occur after Week 12, subjects will complete an ET Visit and the SFU Visit. All subjects who withdraw from the study due to an AE must be followed until resolution of the event or until the event is considered stable. All subjects who withdraw from the study due to development of a laboratory abnormality specified in Criterion #8 must be closely monitored, with additional monitoring of hepatic markers every week or every 2 weeks until resolution of the event, the event is considered stable, or they have reached the end of the SFU Period for those who at any time have an ALT and/or AST  $>5X$  but  $<8X$  ULN.

Investigators should attempt to obtain information on subjects in the case of withdrawal or discontinuation. For subjects considered as lost to follow-up, the Investigator should make an effort (at least 1 phone call and 1 written message to the subject), and document his/her effort (date and summary of the phone call and copy of the written message in the source documents), to complete the final evaluation. All results of these evaluations and observations, together with a narrative description of the reason(s) for removing the subject, must be recorded in the source documents. The electronic Case Report Form (eCRF) must document the primary reason for withdrawal or discontinuation.

Investigators should contact the Medical Monitor, whenever possible, to discuss the withdrawal of a subject in advance.

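### The Week 12 and ET data-collection rule in Protocol 6.3 stops at criterion 10, so it omits criterion 11 (IBD), and its return visit conflicts with the study-withdrawal wording of criterion 9

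*Protocol*

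**What the plan says.** In Protocol Section 6.3, criteria 4 to 11 all fall under one lead-in: "Subjects should be withdrawn from all study treatment if any of the following events occur". The last of them begins "11. Subjects with newly diagnosed inflammatory bowel disease (IBD) or with IBD flares during the study must", and one of its required actions is "Discontinue IMP and be followed-up until resolution of active IBD symptoms".

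The paragraph after the list deals with data collection. A subject who stops study treatment "for any of the above criteria (#4 through #10) prior to Week 12" is asked back for the Week 12 Visit and for the Safety Follow-up (SFU) Visit. The purpose is stated: "These data will be used in a sensitivity analysis which is described in Section 15.7". The next rule, an ET Visit plus the SFU Visit for events after Week 12, refers to the same criteria and so has the same limit.

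Criterion 9, on suicidal ideation or behavior, is inside that range and under the treatment-withdrawal lead-in, yet it ends: "The subject should be referred immediately to a Mental Healthcare Professional and must be withdrawn from the study".

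**The concern.** A rule written to prevent missing Week 12 data should cover every reason for stopping study drug in the list it follows. Here it covers seven of the eight. The one left out was added later, which points to a cross-reference that was not updated. No section gives a reason for a deliberate exclusion.

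What is at stake is the prespecified sensitivity analysis that takes subjects as randomized and uses whatever Week 12 data exist (Protocol 15.7; SAP 8.1.5), together with its pairwise counterpart. Its target is everyone randomized. If one reason for stopping carries no instruction to return, that analysis falls back on nonresponder imputation for exactly the subjects it was meant to observe. The reason is not remote from the drug: Protocol 2.1.1 discusses the role of IL-17 in immune-mediated gut disease, and exclusion criterion 24 admits subjects with inactive Crohn's disease or ulcerative colitis.

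For criterion 9 the problem is ambiguity. A site can treat the subject as having left the study, or as off drug and due back at Week 12.

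**Working it through.** The point rests on reading passages side by side. Arithmetic only bounds its size.

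**1. Coverage of the rule**

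| Criterion (Protocol 6.3) | Under treatment-withdrawal lead-in | Inside the #4–#10 range | Conflict with the return rule |
|---|---|---|---|
| 4, 6, 7, 8 | yes | yes | none found |
| 5 (TB, NTMB) | yes | yes | Section 12.6.5 requires study withdrawal with an ET Visit for active TB or NTMB, and sends latent-TB subjects withdrawn from treatment to the Week 48/ET Visit |
| 9 (suicidality) | yes | yes | its own text orders study withdrawal |
| 10 (HADS-D) | yes | yes | says the subject must be withdrawn, but not from what |
| 11 (IBD) | yes | **no** | no Week 12 or ET instruction |

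**2. Whether another section fills the gap for criterion 11**

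- Protocol 5.1.5 gives the SFU Visit to all who discontinue early, including those withdrawn from treatment. SFU is covered.
- Protocol 5.1.2 gives an ET Visit to subjects withdrawing early from the study. It does not address a subject who stops drug and stays in the study.
- Protocol 15.7 states an aim of collecting Week 12 outcome data for all subjects. It is an aim, not a visit instruction.
- SAP 3.5 treats as Week 12 data the visits of subjects who stop treatment early and return as the protocol provides. It depends on the protocol rule and does not extend it.

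**3. Where the effect can appear**

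- Primary analysis (Protocol 15.3.1; SAP 8.1.2): anyone who stops study treatment before Week 12 is a nonresponder whether or not they return. Change: none.
- All-available-data analysis (Protocol 15.7; SAP 8.1.5): a subject with no Week 12 ACR50 data is assumed a nonresponder. The result differs only if that subject would have been a responder off drug. With 40 per arm, the change per such subject is 1/40 = 2.5 percentage points in that arm.

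**4. Scale against the plan's power figure**

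Protocol 15.9 states power above 99% for a 2-sided 0.05 linear trend test with 40 per arm. Inputs are assumed ACR50 rates of 8%, 15.0%, 42.2% and 58.5%. The TNF adjustment, read as a relative 25% cut in 30% of subjects and applied to the active arms, is 0.7 + 0.3 × 0.75 = 0.925. The rates become 8%, 13.9%, 39.0% and 54.1%. With scores 0 to 3 (mean 1.5):

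- U = 40 × Σp(x − 1.5) = 32.70
- null SD = √[p̄(1 − p̄) × 40 × 5] = 6.40, with p̄ = 0.2876
- alternative SD = √[40 × Σp(1 − p)(x − 1.5)²] = 5.71
- power = Φ[(32.70 − 1.96 × 6.40)/5.71] = Φ(3.53) = 99.98%

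The stated figure reproduces. The documents give no IBD rate, so the counts below are assumptions. They are would-be responders in the 320mg arm with no Week 12 visit:

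| Lost responders | 320mg rate | Trend power |
|---|---|---|
| 0 | 54.1% | 99.98% |
| 1 | 51.6% | 99.95% |
| 2 | 49.1% | 99.88% |
| 3 | 46.6% | 99.73% |

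**The case against.** The best defense is that this is a stale number with little behind it. Section 6.3 opens its data-collection paragraph with a general intention to gather data from early withdrawals, Section 15.7 repeats it for all subjects, and nothing bars a return after IBD. Criterion 11 does not order study exit. It leaves continued participation to judgment, so a subject still in the study has a Week 12 visit on the schedule, and one whose illness also meets criterion 4 is already inside the range. SAP 4.3.2 presumes that everyone reaches a Week 48 or ET visit. SAP 3.5 may also map some ET assessments to Week 12.

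All of that stands as a limit on the consequence. None of it supplies the missing instruction: general aims and mapping rules do not tell a site to bring the subject back.

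A timing argument is also available. Criterion 11 came with Protocol Amendment 2 (09 Mar 2018 in SAP Section 1), and the order of the SAP amendments suggests that most or all subjects may have been past Week 12 by then. This is not established, and the same amendment also revised the Double-Blind dosing interval. It would not touch the missing ET instruction after Week 12.

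A reader might infer three stronger points, which the documents do not support:

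- **Week 12 data after IBD will go uncollected.** The text leaves collection uninstructed; it does not prevent it.
- **IBD safety follow-up is lost.** Criterion 11 itself requires follow-up of symptoms, Section 5.1.5 secures the SFU Visit, and Sections 12.1.3 and 12.1.6 place IBD among the specially monitored events followed to resolution or a stable outcome.
- **Every IBD subject costs 2.5 points.** Only a subject who would have responded off drug moves the rate.

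On criterion 9, it can be said that the paragraph's purpose is to collect data from subjects leaving the study, so a return request fits. That softens the conflict. It does not remove it, because the lead-in, the criterion and Section 5.1.2 still point to different visit paths.

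**Conclusion.** Wrong as written, and minor. The range in the data-collection paragraph of Protocol 6.3 does not match the list it refers to. Subjects stopped for IBD have no explicit Week 12 or ET instruction, and criterion 9 (with criteria 5 and 10) is not aligned with the return rule.

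The size is at most 2.5 points in an arm per affected would-be responder, and only in the analyses using all available Week 12 data. Even three such losses in the 320mg arm leave trend power at 99.7% under the plan's own rates. The primary analysis is untouched. That few subjects would be affected is an assumption, since the documents give no IBD incidence. The 2.5 points assumes 40 per arm and no Week 12 visit. The point still merits correction because it determines who is asked back for a prespecified analysis, and correcting it costs almost nothing.

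**What to change.** Reconcile the criterion range in the data-collection paragraph of Protocol 6.3 with the list above it, so that the Week 12 and ET visits also address criterion 11. SFU needs no extension.

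In the same edit, reconcile the study-versus-treatment wording of criterion 9, the unspecified withdrawal in criterion 10, and the TB and NTMB instructions for criterion 5 in Section 12.6.5 with the return rule, so that each criterion leads to one visit path. This concerns data-collection visits only. No clinical stopping rule needs to change, and no view is taken here on which should prevail.

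The cost is protocol wording, using visits already defined. SAP 3.5 refers to the protocol for the Week 12 return, so it should need no change.

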### **6.3.1 Potential drug-induced liver injury IMP discontinuation criteria**

Subjects with potential drug-induced liver injury (PDILI) must be assessed to determine if IMP must be discontinued. In addition, all concomitant medications and herbal supplements that are not medically necessary should also be discontinued.

The PDILI criteria below require immediate and permanent discontinuation of IMP:

- Subjects with either of the following:
  - ALT or AST  $\geq 5$ xULN
  - ALT or AST  $\geq 3$ xULN and coexisting total bilirubin  $\geq 2$ xULN
  - Subjects with ALT or AST  $\geq 3$ xULN who exhibit temporally associated symptoms of hepatitis or hypersensitivity. Hepatitis symptoms include fatigue, nausea, vomiting, right upper quadrant pain or tenderness. Hypersensitivity symptoms include fever (without clear alternative cause), rash, or eosinophilia (ie,  $>5\%$ ).

The PDILI criterion below allows for subjects to continue on IMP at the discretion of the Investigator.

- Subjects with ALT or AST  $\geq 3$ xULN (and  $\geq 2$ x Baseline) and  $< 5$ xULN, total bilirubin  $< 2$ xULN, and no eosinophilia (ie,  $\leq 5\%$ ), with no fever, rash, or symptoms of hepatitis (eg, fatigue, nausea, vomiting, right upper quadrant pain or tenderness).

Evaluation of PDILI must be initiated as described in Section 12.5.1. If subjects are unable to comply with the applicable monitoring schedule, IMP must be discontinued immediately.

Investigators should attempt to obtain information on subjects in the case of IMP discontinuation to complete the final evaluation. Subjects with PDILI should not be withdrawn from the study until investigation and monitoring are complete. All results of these evaluations and observations, as well as the reason(s) for IMP discontinuation and subject withdrawal (if applicable), must be recorded in the source documents. The CRF must document the primary reason for IMP discontinuation.

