**Table 12-3: Required investigations and follow-up for PDILI**

Laboratory value		Symptoms a of hepatitis of hypersensitivity	Immediate		Follow-up	
ALT or AST	Total bilirubin		Consultation requirements	Actions	Testing	Evaluation
≥3xULN	≥2xULN b	NA	Hepatology consult c Medical Monitor must be notified within 24 hours (eg, by laboratory alert) and subject discussed with Medical Monitor ASAP.	Immediate, permanent IMP discontinuation	Essential: Must have repeat liver chemistry values and additional testing completed ASAP (see Section 12.5.1.4); recommended to occur at the site with HCP.	Monitoring of liver chemistry values at least twice per week until values normalize, stabilize, or return to within baseline values d
≥3xULN	NA	Yes				
≥5xULN	NA	NA	Need for hepatology consult to be discussed. (required if ALT or AST ≥8xULN) Medical Monitor must be notified within 24 hours (eg, by laboratory alert) and subject discussed with Medical Monitor ASAP.	Immediate, permanent IMP discontinuation		
≥3xULN (and ≥2x baseline) and <5xULN (and ≥2x baseline)	<2xULN	No	Discussion with Medical Monitor required. Consider need for hepatology consult if there is no evidence of resolution (see	Further investigation – immediate IMP discontinuation not required (see Section 12.5.1.2). IMP discontinuation required if any of the	Essential: Every attempt must be made to have repeat liver chemistry values and additional testing completed within 48 hours at the site	Monitoring of liver chemistry values at least twice per week for 2 weeks. d • Immediate IMP discontinuation required if liver

This document cannot be used to support any application for marketing authorization therof.

REDACTED COPY

This document cannot be used to support any application for marketing authorization therof.

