**Table 12-3: Required investigations and follow-up for PDILI**

Laboratory value		Symptoms a of hepatitis of hypersensitivity	Immediate		Follow-up	
ALT or AST	Total bilirubin		Consultation requirements	Actions	Testing	Evaluation
			Follow-up requirements). c	
following occur:
 
 
• Subject cannot comply with monitoring schedule.
 
• Liver chemistry values continue to increase
 
• Liver chemistry values remain <math>\geq 3 \times \text{ULN}</math> (and <math>\geq 2 \times</math> baseline) after 2 weeks of monitoring without evidence of resolution
 
	with HCP (see Section 12.5.1.4).	
chemistry values continue to increase.
 
After 2 weeks of monitoring liver chemistry values:
 
 
• Discontinue IMP if levels remain <math>\geq 3 \times \text{ULN}</math> (and <math>\geq 2 \times</math> baseline) without evidence of resolutiond
 
 
Continue to monitor until values normalize, stabilize, or return to within baseline values.d

ALP=alkaline phosphatase; ALT=alanine aminotransferase; AST=aspartate aminotransferase; ASAP=as soon as possible; NA=not applicable; PDILI=potential drug induced liver injury; ULN=upper limit of normal

IMP=investigational medicinal product; NA=not applicable; PDILI=potential drug induced liver injury; ULN=upper limit of normal

a Hepatitis symptoms include fatigue, nausea, vomiting, and right upper quadrant pain or tenderness; hypersensitivity symptoms include eosinophilia (>5%), rash, and fever (without clear alternative cause).

b If the subject also has  $\geq 2 \times \text{ULN}$  ALP, the possibility of an indication of biliary obstruction should be discussed with the Medical Monitor.

c Details provided in Section 12.5.1.1. The local hepatologist is the expert usually consulted by the treating physician for assessment and management of potential hepatic disease. This would usually be a hepatologist, but may be a gastroenterologist.

d Unless an alternative monitoring schedule is agreed by the Investigator and UCB responsible physician. Determination of stabilization is at the discretion of the Investigator in consultation with the hepatologist (as applicable) and UCB responsible physician, as needed.

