### 12.5.1.5 Follow-up evaluation

- Potential drug-induced liver injury events require follow-up monitoring as described in Table 12–3. Monitoring should continue until liver chemistry values normalize, stabilize, or return to baseline. Determination of stabilization is at the discretion of the Investigator in consultation with the hepatologist (as applicable) and UCB responsible physician, as needed.

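### Protocol Section 6.3 and Table 12-3 set different liver-monitoring intervals for the same subjects: every 1 to 2 weeks against at least twice a week

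*Protocol*

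**What the plan says.** Two places in the current protocol text set liver monitoring after study drug is stopped.

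- **Section 6.3, follow-up after withdrawal.** Subjects who withdraw because of a laboratory abnormality under Criterion 8 are to have "additional monitoring of hepatic markers every week or every 2 weeks until resolution of the event". Stability of the event and the end of the SFU Period are given as further end points. The sentence closes with the words "for those who at any time have an ALT and/or AST", followed by the range above 5x but below 8x ULN.
- **Section 6.3, Criterion 8.** The liver part of the criterion is not self-contained: "Subject develops laboratory abnormalities (with or without clinical symptoms) of ALT or AST as defined in Section 6.3.1".
- **Section 6.3.1.** "The PDILI criteria below require immediate and permanent discontinuation of IMP"; the list includes ALT or AST of 5x ULN or more.
- **Section 12.5.1, Table 12-3.** The rows that call for immediate, permanent discontinuation include one for ALT or AST of 5x ULN or more. The follow-up evaluation is "Monitoring of liver chemistry values at least twice per week until values normalize, stabilize, or return to within baseline values".
- **Table 12-3, footnote d.** This qualifies the schedule: "Unless an alternative monitoring schedule is agreed by the Investigator and UCB responsible physician".
- **Section 12.5.1.5.** The table is the required schedule: "Potential drug-induced liver injury events require follow-up monitoring as described in" Table 12-3.

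**The concern.** A subject whose ALT rises to, say, 6x ULN meets Criterion 8, meets the discontinuation criterion in Section 6.3.1 and falls in the 5x ULN row of Table 12-3. Section 6.3 then gives the site one sampling interval and Table 12-3 another. Both are worded as requirements, and the Section 6.3 follow-up paragraph mentions neither the table nor its footnote.

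A site working from Section 6.3 would sample a subject with a marked enzyme rise two to four times less often than Table 12-3 requires, and would deviate from the protocol without knowing it. Sites could also follow comparable subjects differently. The protocol lists liver enzyme elevations among its adverse events for special monitoring (Section 12.1.3), so this is a part of the safety follow-up where uniform conduct matters. No efficacy estimate, error rate or sample size depends on it.

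**Working it through.** The plan states no figure to reproduce. The check is whether the two rules cover the same subjects and, if so, how far apart they are.

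**Step 1. Are the subjects the same?** Criterion 8 sits under withdrawal from study treatment and borrows its ALT/AST limits from Section 6.3.1. That section and Table 12-3 share the threshold of 5x ULN or more and the same action. The range named in Section 6.3, above 5x to below 8x, lies wholly inside the table's row. The table uses 8x only for the consultation requirement: "Need for hepatology consult to be discussed. (required if ALT or AST ≥8xULN". It gives 5x to 8x no schedule of its own.

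**Step 2. Does any row of the table support a 1- to 2-week interval?** No. In the text I worked from, the follow-up cells beside the 5x ULN row are empty. I read the twice-weekly entry as one cell merged across the immediate-discontinuation rows, which can be confirmed in the PDF. The conclusion does not hang on that reading alone: the milder row, 3x to below 5x ULN without symptoms, also asks for at least twice a week for 2 weeks and states no interval after that.

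**Step 3. How far apart are they?**

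| Source | Interval | Tests per week | Tests in 4 weeks |
|---|---|---|---|
| Section 6.3, weekly | 1 week | 1/1 = 1 | 1 x 4 = 4 |
| Section 6.3, 2-weekly | 2 weeks | 1/2 = 0.5 | 0.5 x 4 = 2 |
| Table 12-3 | at least twice per week | at least 2 | at least 2 x 4 = 8 |

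The ratios of Table 12-3 to Section 6.3 are at least 2/1 = 2 and 2/0.5 = 4.

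**Step 4. Do the end points agree?** In part. Resolution or stability ends monitoring under both. Section 6.3 adds the end of the SFU Period. Table 12-3 and Section 12.5.1.5 have no calendar limit, so a subject whose values are still abnormal and unstable when SFU ends would be handled differently.

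**Step 5. What if the 5x to 8x phrase limits only the SFU end point?** The sentence can be read that way. The 1- to 2-week interval would then apply to every liver case under Criterion 8, including those at 8x ULN or more, and the disagreement would be wider.

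**The case against.** The best opposing reading is sequential. Section 6.3 speaks of subjects who withdraw from the study, whereas Table 12-3 concerns a liver event after study drug is stopped. Section 6.3.1 says such subjects should stay in the study until investigation and monitoring are finished. Table 12-3 would then apply first and Section 6.3 afterwards. But Criterion 8 is listed under withdrawal from treatment, not from the study. On the sequential reading, Section 6.3 would also order liver monitoring for subjects whose liver monitoring should already be complete. That too needs resolving.

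Second, Section 6.3 calls its monitoring additional, which could mean on top of the table's schedule. That is possible, but the section does not say so.

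Third, the cross-references already lead to the table: Criterion 8 points to Section 6.3.1, which points to Section 12.5.1, and Section 12.5.1.5 names Table 12-3. This stands as mitigation, since a careful site would probably find the stricter schedule. It does not withdraw the interval printed in Section 6.3.

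Fourth, footnote d permits another schedule. It requires agreement between the investigator and the sponsor's physician, while Section 6.3 states its interval as a general rule with no such condition.

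Finally, the 4-week count assumes values that stay unresolved and unstable for that long with no alternative agreed. That is fair: the count is an illustration, and the ratio per week is the firmer figure. The table also requires notification of the Medical Monitor within 24 hours, which limits the practical risk.

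**Conclusion.** The contradiction is real and lies in current text. For subjects discontinued with ALT or AST between 5x and 8x ULN, the protocol asks for 0.5 to 1 test per week in one place and at least 2 per week in another, a difference of at least two- to four-fold, with an extra end point in Section 6.3. This rests on two readings: that the twice-weekly entry in Table 12-3 covers all its immediate-discontinuation rows, and that Section 6.3 is not meant as a later stage or an add-on, which it does not say. If the 5x to 8x phrase qualifies only the SFU end point, the conflict covers more subjects, not fewer. It should be corrected as a safety-conduct inconsistency; it does not threaten the primary analysis.

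**What to change.** The sponsor should reconcile Section 6.3 with Table 12-3. The simplest form is to keep one agreed monitoring schedule and one stopping rule in Section 12.5.1, and to replace the interval in the Section 6.3 paragraph with a reference to it. If the two schedules are meant for different stages or different enzyme ranges, the text should say which applies to whom and when, whether the SFU limit applies, and how footnote d relates to Section 6.3. The choice of interval belongs to the sponsor's clinical and safety staff, and none is proposed here.

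The cost is protocol wording only, through an amendment or a clarification letter to sites. Design, sample size and SAP are unaffected.
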